### Definition of Life-Threatening

An AE is life-threatening if the subject was at immediate risk of death from the event as it occurred (ie, does not include a reaction that might have caused death if it had occurred in a more serious form). For instance, drug-induced hepatitis that resolved without evidence of hepatic failure would not be considered life-threatening even though drug-induced hepatitis can be fatal.

### Definition of Hospitalization

Adverse events requiring hospitalization should be considered serious. In general, hospitalization signifies that the subject has been detained (usually involving an overnight stay) at the hospital or emergency ward for observation and/or treatment that would not have been appropriate at the study site. When in doubt as to whether hospitalization occurred or was necessary, the AE should be considered as serious.

Hospitalization for elective surgery or routine clinical procedures, which are not the result of an AE, need not be considered AE and should be recorded on a Clinical Assessment Form and added to the electronic Case Report Form. If anything untoward is reported during the procedure, this must be reported as an AE and either 'serious' or 'nonserious' attributed according to the usual criteria.

### **Serious Adverse Event Reporting**

If an SAE occurs, the Investigators will take appropriate action immediately and will strive to identify the causes of the event.

All SAE, irrespective of their causality, will be notified by the Investigator to the pharmacovigilance provider assigned by the Sponsor and the Medical Monitor in writing using the "Serious Adverse Event Report Form" (eg, by email or facsimile) within 24 hours of when an SAE is first recognized or reported.

**Email:** [REDACTED]

**Fax:** [REDACTED]

The provided information shall contain as much detail regarding the event as is available at the time. Investigators shall not wait to receive additional information to fully document the event, before notifying the SAE at the initial notification. Subsequently, a full written report of the SAE will be sent to the pharmacovigilance provider and Medical Monitor within 3 working days of the original notification. Further follow-up reports will be provided when new information becomes available. Where applicable, information from relevant hospital records or autopsy reports should be obtained, if possible, and provided to the pharmacovigilance provider assigned by the Sponsor and the Medical Monitor.

Food and Drug Administration (FDA)-reportable SAE will be reported to FDA by the pharmacovigilance provider on behalf of the Sponsor using FDA Form 3500A or equivalent within the timeframe required by the FDA.

The responsible Institutional Review Board (IRB) will be notified of any FDA-reportable SAE within the timeframe required by the IRB. The IRB Serious and Unexpected Adverse Experience Submission Form will be completed and submitted with the copy of the written confirmation or summary of the AE.

### **Pregnancy**

Pregnancy in itself is not considered an AE, unless there is a suspicion that the IMP may have interfered with the effectiveness of a contraceptive medication. However, complications of pregnancy and abnormal outcomes of pregnancy are considered AE, and many may meet criteria for an SAE. Complications of pregnancy and abnormal outcomes of pregnancy, such as ectopic pregnancy, spontaneous abortion, intrauterine fetal demise, neonatal death, or congenital anomaly, would meet the criteria of an SAE and therefore should be reported as an SAE. Elective abortions without complications should not be handled as an AE.

All pregnancies (even if suspected) must be reported on the appropriate CRF page (Pregnancy Form) within 24 hours of the time that the investigator became aware of the

pregnancy (or suspected pregnancy). In any case, each pregnancy should be followed until its termination (either by birth of a child or abortion) and the CRF Pregnancy Form should be updated.

**Appendix 2: Clinical Laboratory Evaluations**

Clinical chemistry:	Hematology:	Urinalysis:
Alanine aminotransferase Albumin Alkaline phosphatase Aspartate aminotransferase Blood urea nitrogen Calcium Chloride Cholesterol Creatinine Gamma-glutamyl transferase Glucose Potassium Sodium Total bilirubin a Total CO 2 (measured as bicarbonate) Total protein Uric acid	Hematocrit Hemoglobin Mean cell hemoglobin Mean cell hemoglobin concentration Mean cell volume Platelet count Red blood cell (RBC) count White blood cell (WBC) count WBC differential: Basophils Eosinophils Lymphocytes Monocytes Neutrophils	Bilirubin Blood Color and appearance Glucose Ketones Leukocyte esterase Nitrite pH Protein Specific gravity Urobilinogen Microscopic examination (if protein, leukocyte esterase, nitrite, or blood is positive)
Serologyb:	Drug screenc:	Hormone panel - women only:
Hepatitis B surface antigen Hepatitis C antibody Human immunodeficiency (HIV-1 and HIV-2) antibodies	Including but not limited to: Amphetamines/methamphetamines Barbiturates Benzodiazepines Cocaine (metabolite) Methadone Phencyclidine Opiates Tetrahydrocannabinol/ cannabinoids	Follicle-stimulating hormone (postmenopausal women only) b Pregnancy test (human chorionic gonadotropin) c

a Direct bilirubin will be analyzed if total bilirubin is elevated.

b Only analyzed at Screening.

c Blood pregnancy testing will be performed at Screening and Safety Follow-up visit and urine pregnancy testing will be performed at Day 1 predose in women of childbearing potential only. If there is doubt over the accuracy of a positive urine pregnancy test result, a blood pregnancy test must be obtained through the central laboratory to confirm the result. A local blood pregnancy test may also be performed if considered to be in the best interest of the subject (eg, travel planning).

**Appendix 3: Total Blood Volume**

The maximum blood volume to be withdrawn per subject (Part A or Part B), including all scheduled blood draws and any unscheduled blood draws that may be needed for subject safety, will not exceed [REDACTED] mL.

## Appendix 4: Regulatory, Ethical, and Study Oversight Considerations

### Regulatory and Ethical Considerations

This study will be conducted in accordance with the protocol and with the following:

- Consensus ethical principles derived from international guidelines including the Declaration of Helsinki and Council for International Organizations of Medical Sciences (CIOMS) International Ethical Guidelines.
- Applicable International Conference on Harmonisation (ICH) Good Clinical Practice (GCP) Guidelines.
- Applicable laws and regulations.

The protocol, protocol amendments, Informed Consent Form (ICF), Investigator Brochure, and other relevant documents (eg, advertisements) must be submitted to an Institutional Review Board (IRB) by the Investigator and reviewed and approved by the IRB before the study is initiated.

Any amendments to the protocol will require IRB and regulatory authority (as locally required) approval before implementation of changes made to the study design, except for changes necessary to eliminate an immediate hazard to study subjects.

The Investigator will be responsible for the following:

- Providing written summaries of the status of the study to the IRB annually or more frequently in accordance with the requirements, policies, and procedures established by the IRB.
- Notifying the IRB of serious adverse events or other significant safety findings as required by IRB procedures.
- Providing oversight of the conduct of the study at the site and adherence to requirements of 21 Code of Federal Regulations (CFR), ICH guidelines, the IRB, European regulation 536/2014 for clinical studies (if applicable), and all other applicable local regulations.

### Finances and Insurance

Financing and insurance will be addressed in a separate agreement.

### Informed Consent

Prior to starting participation in the study, each subject will be provided with a study-specific ICF giving details of the study drugs, procedures, and potential risks of the study. Subjects will be instructed that they are free to obtain further information from the Investigator and that their participation is voluntary and they are free to withdraw from the study at any time. Subjects will be given an opportunity to ask questions about the study prior to providing consent for participation.

Following discussion of the study with site personnel, subjects will sign 2 copies of the ICF in the presence of a suitably trained member of staff to indicate that they are freely giving their informed consent. One copy will be given to the subject, and the other will be maintained in the subject's records.

Subjects must be re-consented to the most current version of the ICF(s) during their participation in the study.

### **Subject Data Protection**

Subjects will be assigned a unique identifier and will not be identified by name in Case Report Forms (CRF), study-related forms, study reports, or any related publications. Subject and Investigator personal data will be treated in compliance with all applicable laws and regulations. In the event the study protocol, study report, or study data are included in a public registry, all identifiable information from individual subjects or Investigators will be redacted according to applicable laws and regulations.

The subject must be informed that his/her personal study-related data will be used by the Sponsor in accordance with local data protection law. The level of disclosure must also be explained to the subject. The subject must also be informed that his/her study-related data may be examined by Sponsor or Contract Research Organization (CRO) auditors or other authorized personnel appointed by the Sponsor, by appropriate IRB members, and by inspectors from regulatory authorities.

### **Disclosure**

All information provided regarding the study, as well as all information collected and/or documented during the course of the study, will be regarded as confidential. The Investigator agrees not to disclose such information in any way without prior written permission from the Sponsor.

### **Data Quality Assurance**

The following data quality steps will be implemented:

- All subject data relating to the study will be recorded on CRF unless directly transmitted to the Sponsor or designee electronically (eg, laboratory data). The Investigator is responsible for verifying that data entries are accurate and correct by electronically signing the CRF.
- The Investigator must maintain accurate documentation (source data) that supports the information entered in the CRF.
- The Investigator must permit study-related monitoring, audits, IRB review, and regulatory agency inspections and provide direct access to source data documents.
- The Sponsor or designee is responsible for the data management of this study including quality checking of the data. Predefined, agreed risks, monitoring thresholds, quality tolerance thresholds, controls, and mitigation plans will be documented in a risk management register. Additional details of quality checking to be performed on the data may be included in a Data Management Plan.

- A Study Monitor will perform ongoing source data verification to confirm that data entered into the CRF by authorized site personnel are accurate, complete, and verifiable from source documents; that the safety and rights of subjects are being protected; and that the study is being conducted in accordance with the currently approved protocol and any other study agreements, ICH GCP, and all applicable regulatory requirements.
- Records and documents, including signed ICFs, pertaining to the conduct of this study must be retained by the Investigator in accordance with 21 CFR 312.62(c) unless local regulations or institutional policies require a longer retention period. No records may be destroyed during the retention period without the written approval of the Sponsor. No records may be transferred to another location or party without written notification to the Sponsor.

### **Investigator Documentation Responsibilities**

All individual, subject-specific study data will also be entered into a 21 CFR Part 11-compliant electronic data capture (EDC) system on a CRF in a timely fashion.

All data generated from external sources (eg, laboratory and bioanalytical data), and transmitted to the Sponsor or designee electronically, will be integrated with the subject's CRF data in accordance with the Data Management Plan.

A CRF must be completed for each subject who signs an ICF and undergoes any screening procedures, according to the CRF completion instructions. The Sponsor, or CRO, will review the supporting source documentation against the data entered into the CRF to verify the accuracy of the electronic data. The Investigator will ensure that corrections are made to the CRF and that data queries are resolved in a timely fashion by the study staff.

The Investigator will sign and date the CRF via the EDC system's electronic signature procedure. These signatures will indicate that the Investigator reviewed and approved the data on the CRF, data queries, and site notifications.

### **Publications**

If on completion of the study the data warrant publication, the Investigator may publish the results in recognized (refereed) scientific journals subject to the provisions of the clinical study agreement (CSA). Unless otherwise specified in the CSA, the following process shall occur:

If the Investigator expects to participate in the publication of data generated from this site, he or she must obtain prior approval of the Sponsor before submission for publication or presentation.

**Appendix 5: Schedule of Assessments**

**Table 1: Schedule of Assessments – Part A (Single Dose)**

Study Epoch	Screening	Treatment			Follow-up	
Study Procedures	Screening	Day 1 predose	Day 1 dosing & postdose	Days 2 & 3	Safety Follow-up	Additional Follow-up
Study Day (Window)	-28 to -1	1	1	2 & 3	7 (+3)	14 (±3)
Informed consent	X					
Inclusion/exclusion criteria	X	X				
Demographic data a	X					
Medical history	X	X b				
Body weight and height	X				X c	
Oral body temperature	X	X d	X	X	X	X
Blood pressure and pulse rate	X	X d	X e	X	X	X
SpO 2	X	X d	X e	X	X	X
Physical examination	X	X	X f	X f	X f	X f
Pregnancy test g	X	X			X	
Follicle-stimulating hormone h	X					
12-lead ECG	X	X	X i	X	X	
HRCT	X j					
Spirometry k	X	X l	X l	X	X	X
Carbon monoxide diffusion capacity k	X	X d		X	X	X
Clinical chemistry and hematology	X	X		Day 3 only	X	
Serology	X					
Urine drugs of abuse screen m	X					
██████████ ██████████		██████████	██████████	██████████		
Nonresidential visit	X			Day 3 only	X	X
Study treatment administration			X			
Adverse event recording		X	X	X	X	X
██		██████████				
Pharmacokinetic blood sampling		X	X o			
██		██████████			██████████	██████████

Note, where multiple assessments are required at a single timepoint, the following order of procedures should be used: blood sampling, spirometry, other procedures (ECGs should be scheduled before vital signs measurements). See also footnote k.

Note, timing of safety and pharmacokinetic assessments may be changed based upon findings from previous cohorts.

Abbreviations: ECG = electrocardiogram; HRCT = high-resolution computed tomography; SpO2 = oxygen saturation.

- a To include smoking history.
- b Interim medical history.
- c Height measured only at Screening.
- d Within 60 minutes prior to dosing.
- e 1 hour and 2 hours after completion of dose administration.
- f Symptom-directed physical examination.
- g In women of childbearing potential. Blood pregnancy test will be performed at Screening and Safety Follow-up; urine pregnancy test will be performed at Day 1. If the Day 1 pregnancy test is positive, dosing of that subject should not proceed. If there is doubt over the accuracy of a positive urine pregnancy test result, a blood pregnancy test must be obtained through the central laboratory to confirm the result. A local blood pregnancy test may also be performed if considered to be in the best interest of the subject (eg, travel planning). If the local test is negative and there are no other clinical findings suggestive of pregnancy, the subject may be dosed.
- h In postmenopausal women (at least 12 months postcessation of menses without an alternative medical cause) only, to confirm postmenopausal status. Confirmation of postmenopausal status requires level >40 mIU/mL in addition to appropriate history (refer to [Section 6.5](#)).
- i 2 hours after completion of dose administration.
- j If the most recent historical HRCT was performed more than 12 months prior to the initiation of Screening OR if the HRCT performed within 12 months prior to the initiation of Screening is determined not to be of suitable quality by the central over-reader, the imaging study must be repeated during Screening. Any HRCT used to establish subject eligibility must undergo central interpretation.
- k Spirometry should preferably be performed before carbon monoxide diffusion capacity assessments at timepoints where both assessments are required, but if not feasible, the rationale should be documented in source records and the order of testing implemented on Day 1 should be used at every subsequent study visit.
- l Completion of a minimum of 3, maximum of 6 forced expiratory maneuvers within 60 minutes predose. Preferably 3 but a minimum of 2 maneuvers as soon as feasible but within 15 minutes after completion of dose administration and at 30 ± 5 minutes, 60 ± 10 minutes, and 90 ± 15 minutes after completion of dose administration (up to a maximum of 16 forced expiratory maneuvers per day).
- m Exclusionary only if positive for a drug or metabolite of a drug that has not been prescribed and that remains positive on repeat testing.
- n [REDACTED]
- o Within 5 minutes after completion of dose administration and 10, 30, and 60 minutes after completion of dose administration, to assay for parent drug (TRK-250). PK sampling times are given as targets to be achieved within reasonable limits (eg, ±10%).

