### 2.2. Endpoints

#### 2.2.1. Primary Endpoints

The primary safety endpoints for this study are as follows:

- body weight
- vital signs measurements

- oxygen saturation (SpO2) by pulse oximetry
- hematology, clinical chemistry, and urinalysis test results
- 12-lead electrocardiogram (ECG) parameters
- forced expiratory volume over 1 second (FEV1), forced vital capacity (FVC)
- incidence and severity of adverse events (AE)

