### 3.1. Overall Study Design and Plan

#### 3.1.1. Part A

Part A will comprise a single-dose, single-period, sequential-cohort study. Potential subjects will be screened to assess their eligibility to enter the study within 28 days prior to study drug administration.

The total duration of study participation for each subject (from Screening through Additional Follow-up visit) is planned to be no more than 7 weeks but may be increased to a maximum

of 9 weeks if the Additional Follow-up visit is delayed based on findings from the ongoing review of data by the data monitoring committee (DMC).

It is planned that 16 subjects will be studied in 4 cohorts (Cohorts A1 to A4), each consisting of 4 subjects. Following DMC review of the safety and tolerability data from the first 4 cohorts, up to 3 further optional cohorts (Cohorts A5 to A7) of at least 4 subjects may be added to Part A to evaluate additional doses or to further evaluate planned doses.

[REDACTED]

[REDACTED]

All subjects will return for a Safety Follow-up visit 7 (+3) days after dosing and an Additional Follow-up visit 14 ( $\pm 3$ ) days after dosing. The timing of the Additional Follow-up visit for a cohort may be changed to a maximum of 28 ( $\pm 3$ ) days after dosing, based on emerging safety data.

In each of Cohorts A1 to A4, 3 subjects will receive TRK-250 and 1 subject will receive placebo. All doses will be administered in accordance with a randomization schedule on the morning of Day 1. Each subject will receive only a single dose of TRK-250 or placebo during the study. [REDACTED]

[REDACTED]

[figure not shown]
- Cohort A1: 2 mg
- Cohort A2: 10 mg
- Cohort A3: 30 mg
- Cohort A4: 60 mg

[REDACTED]

[REDACTED] pharmacologically active dose levels (ie, when the escalated dose will be  $\geq 34.7$  mg).

An overview of the study design and the planned dose levels are shown in [Figure 1](#).

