**Figure 1: Study Schematic (Part A)**

**3.1.2. Part B**

Part B will comprise a multiple-dose, single-period, sequential-cohort study. Potential subjects will be screened to assess their eligibility to enter the study within 28 days prior to initial study drug administration.

The total duration of study participation for each subject (from Screening through Safety Follow-up visit) is planned to be no more than 10 weeks but may be increased to a maximum of 12 weeks if the Additional Follow-up visit is delayed based on findings from the ongoing review of data by the DMC.

[REDACTED]

[REDACTED]

[figure not shown]
All subjects will return for a Safety Follow-up visit approximately 7 days after their last dose (Day 29 [+3]) and an Additional Follow-up visit approximately 14 days after the last dose (Day 36 [ $\pm$ 3]). The timing of the Additional Follow-up visit for a cohort may be changed to a maximum of approximately 28 days after the last dose (Day 50 [ $\pm$ 3]), based on emerging safety data.

In each of Cohorts B1 to B3, 4 subjects will receive TRK-250 and 2 subjects will receive placebo. Doses will be administered on the morning of Days 1, 8, 15, and 22 in accordance with a randomization schedule. Each subject will receive 4 once-weekly doses of TRK-250 or placebo during the study. [REDACTED]

[REDACTED]

- Cohort B1: 10 mg
- Cohort B2: 30 mg
- Cohort B3: 60 mg

[REDACTED] shown in [Figure 2](#).

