#### **7.1.6. Body Weight and Height**

Body weight (in underclothes) and height will be recorded at the times indicated in the Schedule of Assessments in [Appendix 5](#).

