10.1.1 Definition of Baseline and Change from Baseline

Baseline for each parameter is defined as the last value measured prior to dosing, including repeat (vital signs and electrocardiograms [ECGs]) and unscheduled (clinical laboratory parameters) readings (see Section 10.1.2 for definitions of repeat and unscheduled readings). For vital signs taken in triplicate, baseline will be the median of the last 3 values taken prior to dosing. For ECGs taken in triplicate, baseline will be the mean of the last 3 values taken prior to dosing.

Mean change from baseline is the mean of all individual subjects' change from baseline values. Each individual change from baseline will be calculated by subtracting the individual subject's baseline value from the value at the timepoint. The individual subject's change from baseline values will be used to calculate the mean change from baseline using a SAS procedure such as Proc Univariate.

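### Body weight is a primary safety endpoint with no Day 1 measurement, so the only weight change that could be formed starts 1 to 28 days before the first dose

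*Protocol*

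**What the plan says.** Protocol Section 2.2.1 opens its list with "The primary safety endpoints for this study are as follows", and body weight is the first item. Section 7.1.6 leaves the timing entirely to the schedule: "Body weight (in underclothes) and height will be recorded at the times indicated in the Schedule of Assessments in" Appendix 5.

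In Appendix 5, the row "Body weight and height" has the same pattern in Table 1 (Part A) and Table 2 (Part B): one mark at Screening and one at Safety Follow-up. The footnote on the follow-up mark reads "Height measured only at Screening", so that entry is for weight alone. No weight is scheduled on Day 1, on Days 2 and 3 in Part A, on Days 8, 15 or 22 in Part B, or at Additional Follow-up.

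By contrast, temperature, blood pressure, pulse rate, SpO2, ECG, spirometry, DLCO, clinical chemistry and hematology each have a Day 1 predose mark in both tables.

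SAP 10.1.1 states: "Baseline for each parameter is defined as the last value measured prior to dosing". SAP 10.6 has no subsection on body weight. Under 10.6.8, safety assessments not covered in that section are listed without summary. SAP 10.2 summarizes weight only as a demographic variable.

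**The concern.** A change score is meant to describe what happened after treatment began. For weight, the starting value may be up to four weeks old at the first dose, and its age differs from subject to subject. Two subjects with the same recorded change may have spent very different fractions of the interval on study treatment.

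In a first-in-human trial with 3 active subjects per Part A cohort and 4 per Part B cohort, individual readings matter. Suppose a weight loss is seen at Safety Follow-up. Appendix 1 bases causality partly on timing relative to administration. SAP 10.6.1 separates events that worsened after dosing from those already present. With no weight on Day 1, nothing shows whether the loss began before dosing. The missing value cannot be recovered later.

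For spirometry and DLCO the protocol takes Day 1 as baseline and uses Screening only when the Day 1 test is inadequate and the subject has been dosed (Sections 7.1.8 and 7.1.9). Weight has only the second-choice value.

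**Working it through.** **Inputs**
- Screening window: Day -28 to -1 in both parts (Appendix 5). Section 3.1.1 agrees: "Potential subjects will be screened to assess their eligibility to enter the study within 28 days prior to study drug administration".
- Part A follow-up weight: "All subjects will return for a Safety Follow-up visit 7 (+3) days after dosing", that is, 7 to 10 days after dosing.
- Part B follow-up weight: Day 29 (+3), that is, 28 to 31 days after the first dose on Day 1 (Section 3.1.2).
- Day numbering has no Day 0, so the time from Day -k to Day d is k + d - 1 days, of which k precede the first dose.

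**Check on the plan's own figures.** The documents contain no sample-size calculation to reproduce. The stated maximum participation times depend on the same window. From Day -28 to the latest Additional Follow-up:
- Part A: 28 + 14 + 3 = 45 days (6.4 weeks; stated limit 7). Extended: 28 + 28 + 3 = 59 days (8.4; limit 9).
- Part B: 28 + 39 - 1 = 66 days (9.4; limit 10). Extended: 28 + 53 - 1 = 80 days (11.4; limit 12).

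All four fit, so the day counting agrees with the protocol.

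**Share of the weight-change interval before the first dose** = k / (k + days from first dose to follow-up)

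| Screening interval k | Part A (7 to 10 days) | Part B (28 to 31 days) |
|---|---|---|
| 28 days (maximum) | 28/35 = 80% to 28/38 = 74% | 28/56 = 50% to 28/59 = 47% |
| 14.5 days (mid-window) | 14.5/21.5 = 67% to 14.5/24.5 = 59% | 14.5/42.5 = 34% to 14.5/45.5 = 32% |
| 1 day (minimum) | 1/8 = 13% to 1/11 = 9% | 1/29 = 3% to 1/32 = 3% |

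If the Part A schedule entry is read literally as Study Day 7 to 10, follow-up is 6 to 9 days after dosing. The maximum share is then 28/34 = 82% to 28/37 = 76%.

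**Illustration in kilograms, on an assumption only.** The documents give no rate of weight drift. With an assumed common drift of 0.1 to 0.5 kg/week, 28 pre-dose days contribute 0.4 to 2.0 kg. If Screening intervals were uniform on 1 to 28 days, their SD would be sqrt((28² - 1)/12) = 8.08 days. The SD of a group difference caused by chance imbalance in those intervals would be:
- Part A, 3 active vs 4 placebo: 8.08 × sqrt(1/3 + 1/4) = 6.2 days, or 0.09 to 0.44 kg.
- Part B, 4 active vs 6 placebo: 8.08 × sqrt(1/4 + 1/6) = 5.2 days, or 0.07 to 0.37 kg.

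These values scale directly with the assumed drift. They have not been set against the ordinary variation between two weighings, which a Day 1 weight would not remove.

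**The case against.** A reader might infer that the schedule biases the comparison of TRK-250 with placebo, or that a misleading weight effect will be reported. The documents do not support either reading. Active and placebo subjects in a cohort share the same Screening window and are randomized, so pre-dose change cancels in expectation and only chance noise remains. The SAP also plans no weight-change summary, no group comparison of weight and no inferential safety analysis. The kilogram figures above therefore describe a comparison that nobody has planned, at a drift rate with no source in the documents.

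The plan is not contradictory either. Section 7.1.6 defers to Appendix 5, and SAP 10.1.1 yields an unambiguous baseline. The largest shares also require Screening at the very start of the window.

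The lost information can be partly offset. Each subject's Screening interval can be shown beside the listed weights, and both schedules allow the timing of safety assessments to change after earlier cohorts.

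All of this stands and limits the size of the problem. What it leaves is the mixing of pre-treatment and on-study change within each subject, which affects a listing as much as a table. Showing the interval makes that mixing visible but does not separate the two parts. No Day 1 weight is currently planned, and a later schedule change would not repair cohorts already completed.

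**Conclusion.** The point holds as a minor weakness of the schedule. The only weight change that could be formed for this primary safety endpoint begins 1 to 28 days before the first dose. The pre-dose share ranges from about 9% to 80% in Part A and from about 3% to 50% in Part B, depending on when each subject was screened. These shares follow from the visit windows alone. Any figure in kilograms rests on an assumed drift and is illustrative.

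The consequence is a confounded within-subject change and added noise in very small cohorts, not systematic bias between arms. That the SAP lists weight without summarizing it is a separate matter; this point concerns only when weight is measured.

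**What to change.** In Appendix 5 Tables 1 and 2, mark body weight at Day 1 predose, measured as Section 7.1.6 describes. Keep height at Screening only. Table 2 has one predose column for all four dosing days, so the entry there should say Day 1 only, as the pregnancy-test row already does.

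No new baseline wording is needed. The rule in SAP 10.1.1 would take the Day 1 weight as baseline and use the Screening weight if it is missing. The pre-treatment part of the interval falls from 1 to 28 days to zero, leaving 7 to 10 days in Part A and 28 to 31 in Part B.

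The cost is one extra weighing per subject at a visit that already includes a predose physical examination, one schedule cell per table and one CRF field. No visit is added. For any subject dosed without a Day 1 weight, list the number of days from the Screening weight to the first dose beside the weights.
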